14.6. Reporting Period and Monitoring of Patients with Adverse Events

As described in [Section 14.5](#), all AEs must be recorded in the CRF up until the end of the treatment period. All patients who took at least one dose of study drug, whether they completed the treatment period or not, should complete the end of treatment procedures.

All AEs will be followed until clinical database lock (or resolution if it occurs before database lock). All SAEs will undergo active follow up until resolved or the event becomes chronic or stable. Follow up data for SAEs obtained after clinical database lock will be incorporated into the ACE-536 safety database.

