14.5. Documentation and Methods of Reporting of Adverse Events by Investigator

It is the responsibility of the Investigator to document all AEs that occur during the study. Patients will be evaluated and questioned generally for AEs during the course of the study, starting at the signing of the informed consent. The Investigator must report in detail all adverse signs and symptoms which are either volunteered by patients or observed during or following the course of investigational product administration on the appropriate CRF page. For patients

without treatment interruption, any AE ongoing at the time of EOT in A536-04 needs to be re-entered as an AE in A536-06. For patients with treatment interruption, all non-serious AEs occurring after signing of the ICF until a patient is dosed on C1D1 are to be documented on the medical history CRF. All AEs and SAEs occurring after the Cycle 1 Day 1 dose through 56 days after the last study drug administration (EOS visit) are to be reported and documented on the AE CRF.

All AEs spontaneously reported by the patient and/or in response to an open question from study personnel or revealed by observation, physical examination or other diagnostic procedures will be recorded on the AE CRF. Any clinically relevant changes in laboratory assessments, or other clinical findings as described in [Section 14.1](#), are considered AEs and must be recorded on the AE CRF. AEs are to be followed for resolution as described in Section 14.6.

It is important that each AE report include a description of the event, duration (onset and resolution dates), severity, relationship with ACE-536, any other potential causal factors, any treatment given or other action taken (including dose modification or discontinuation of ACE-536) and outcome. In addition, serious AEs (SAEs) should be identified and the appropriate seriousness criteria documented. AEs categorized as SAEs must also be documented using an SAE Report Form as described in Section 14.5.1.

Specific guidance can be found in the CRF Completion Guidelines provided by the Sponsor or designee.

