14.5.1. Documentation of Serious Adverse Events

All SAEs that occur after the first study drug administration on Cycle 1 Day 1 until 56 days after the last study drug administration (EOS visit) are to be documented on the AE CRF. SAEs should not be reported for patients who are considered screen failures unless the event is deemed due to a protocol required procedure.

For all SAEs, an SAE form must be completed with as much information as possible and submitted within the time frame described in [Section 14.7](#).

When new significant information is obtained as well as when the outcome of an event is known, the investigator should record the information on a new SAE form. If the patient was hospitalized, a copy of the discharge summary must be included as part of the patient medical file. In all instances, the investigator should follow up with patients until the outcome of the SAE is known.

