14.7. Notification about Serious Adverse Events

If an SAE occurs during the reporting period, the investigator must immediately (i.e. within a maximum 24 hours after becoming aware of the event) inform the sponsor via the CRO by telephone, fax, or e-mail.

All written reports should be transmitted using the study specific SAE Report Form, which must be completed by the investigator following specific completion instructions. Names, addresses, telephone and fax numbers for SAE reporting are located on the SAE Report Form and in the completion instructions provided in the Study Manual. When an SAE (or follow up information) is reported by telephone, a written report must be sent immediately thereafter by fax or e-mail. Reporting procedures and timelines for follow up information are the same as for the initially reported SAE.

Relevant pages from the CRF may be provided in parallel (e.g., medical history, concomitant therapy). In all cases, the information provided in the SAE Report Form must be consistent with the data that are recorded in the corresponding sections of the CRF.

The investigator/reporter must respond to any request for follow up information or to any question the Sponsor or designee may have on the AE within the same timelines as described for initial reports. This is necessary to permit a prompt assessment of the event by the Sponsor and (as applicable) to allow the Sponsor to meet regulatory timelines associated with expedited reporting obligations.

Requests for follow up will usually be made by the responsible clinical research associate or Medical Monitor, or an Acceleron pharmacovigilance representative who may contact the investigator directly to obtain clarification on a particularly critical event.

14.7.1. Safety Reporting to Health Authorities, Independent Ethics Committees Institutional Review Boards and Investigators

The Sponsor will send appropriate safety notifications to Health Authorities in accordance with applicable laws and regulations.

The investigator must comply with any applicable site-specific requirements related to the reporting of SAEs involving his/her patients to the IEC that approved the study.

In accordance with ICH and GCP guidelines, the Sponsor will inform the investigator of “findings that could adversely affect the safety of patients, impact the conduct of the study, or alter the IEC’s approval/favorable opinion to continue the study.”

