5.8.1. Adverse Events

For patients with treatment interruption, all non-serious AEs occurring after signing of the ICF until a patient is dosed on C1D1 are to be documented on the medical history CRF. All AEs and SAEs occurring after the Cycle 1 Day 1 dose through 56 days after the last study drug administration are to be reported and documented on the AE CRF. All AEs collected in this study are treatment emergent adverse events (TEAE). A drug-related TEAE is defined as any TEAE related to the study medication as assessed by the investigator or with missing assessment of the causal relationship.

The following summaries will be presented for all dosed:

- Number and percentage of patients reporting each AE, categorized by System Organ Class (SOC) and Preferred Term (PT)
- Number and percentage of patients reporting each AE experienced by $\geq 5\%$ and $\geq 10\%$ of patients in all patients by PT
- Number and percentage of patients reporting SAE, categorized by SOC and PT
- Number and percentage of patients reporting Grade ≥ 3 AE, categorized by SOC and PT
- Number and percentage of patients reporting related AE, categorized by SOC and PT
- Number and percentage of patients reporting AE leading to drug withdrawal, categorized by SOC and PT
- Number and percentage of AE of interests by cycle

Note that counting will be by patient, not event, and patients are only counted once within each SOC or PT. If a patient experiences the same AE at more than one severity, or with more than one relationship to study drug, the most severe rating or the stronger causal relationship to study drug will be given precedence. Any missing severity, causality, or outcome will not be imputed and classed as unknown.

All AEs will be listed. The following listings will also be provided: 1) patients with SAEs; 2) patients with Grade ≥ 3 AEs; and 3) patients with AEs leading to study drug discontinuation; 4) death.

Concomitant medication use, severity, time to the worst CTCAE grade and recovery will be listed and summarized.

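### Protocol 14.6 misstates 14.5: it ends AE recording at the end of treatment, while 14.5 and SAP 5.8.1 run it through 56 days after the last dose

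*Protocol*

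**What the plan says.** Four places set the end of AE recording.

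- Protocol 14.6, whose title announces the reporting period, refers back to 14.5 and then states that "all AEs must be recorded in the CRF up until the end of the treatment period". It gives no day count.
- Protocol 14.5, the section it refers to, puts on the AE CRF "All AEs and SAEs occurring after the Cycle 1 Day 1 dose through 56 days after the last study drug administration".
- Protocol 14.5.1 repeats the limit for SAEs only: "until 56 days after the last study drug administration (EOS visit) are to be documented on the AE CRF".
- SAP 5.8.1 takes over the 14.5 window for AEs and SAEs, and adds: "All AEs collected in this study are treatment emergent adverse events (TEAE").

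Protocol 14.7 attaches 24-hour SAE notification to the reporting period without giving its length. Protocol 11.3 has a separate rule: new malignancies and premalignant lesions are reported as SAEs through 3 years of follow-up. Protocol 12.3 places the EOT visit 28 ± 7 days after the last dose, or at discontinuation for patients who stop early.

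**The concern.** Sections 14.5 and 14.6 should state the same window, and they do not. An EOT visit held within its window falls on day 35 at the latest, so a treatment period that ends there is over before day 56. A site that reads only 14.6 can close AE entry at EOT and consider itself compliant. A site that reads 14.5 continues to day 56.

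Safety is the primary objective, and Protocol 15.2.2 makes the summary of all AEs part of the primary analysis. An AE that was never entered cannot be recovered at analysis. Because SAP 5.8.1 equates collected with treatment emergent, the tables would combine patients observed for different lengths of time after the last dose without showing it.

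**Working it through.** The plan gives no figure to reproduce, and there is no sample size calculation or hypothesis test. The check compares the texts and subtracts the windows.

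**Inputs.** AE window: 56 days after the last dose (Protocol 14.5, SAP 5.8.1). EOT: day 28, range 21 to 35 (Protocol 12.3). Dosing: every 3 weeks, up to 87 cycles (Protocol 10.1). Exposure convention: last dose + 21 days (SAP 5.5). EOS: about 3 years after the last dose (Protocol 12.6). As a check on the 21-day spacing, Cycle 87 Day 1 is 1 + 86 × 21 = Day 1807, which matches the schedule of events.

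**Days omitted under 14.6.** Gap = 56 − e, where e is the day after the last dose on which the treatment period is taken to end. Section 14.6 does not fix e, so each reading is an assumption:

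- EOT at day 28: 56 − 28 = 28 days
- EOT at day 35 or day 21: 21 or 35 days
- last dose + 21: 35 days
- last dose itself: 56 days, the upper bound

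**Share of the A536-06 recording window.** Share = gap / ((n − 1) × 21 + 56) for n doses without delay.

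| Doses | Window (days) | EOT at day 28 | EOT at day 35 to day 21 | Ends at last dose |
|---|---|---|---|---|
| 1 | 56 | 28/56 = 50% | 37.5% to 62.5% | 100% |
| 5 | 140 | 28/140 = 20% | 15% to 25% | 40% |
| 17 | 392 | 28/392 = 7.1% | 5.4% to 8.9% | 14.3% |
| 87 | 1,862 | 28/1,862 = 1.5% | 1.1% to 1.9% | 3.0% |

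**The label on day 56.** Sections 14.5 and 14.5.1 call day 56 the EOS visit. Protocol 12.6 and SAP 5.1 put EOS about 3 years after the last dose: 3 × 365.25 − 56 ≈ 1,040 days later. Protocol 9.4 and SAP 3.2 instead give early discontinuers an EOS about 28 days after an EOT held at discontinuation. If that EOT falls d days after the last dose, EOS falls on day d + 28, which equals 56 only when d = 28. A site that follows the label instead of the day count therefore has a different end point again. The scheduled visit nearest day 56 is PTFU, at 2 months ± 7 days (Protocol 12.4).

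**The case against.** The best reply is that 14.6 sets no rule of its own. It defers to 14.5 and does not forbid later recording, and the rest of the protocol points past EOT: the schedule of events lists AEs as collected continuously, its AE footnote has patients monitored throughout the study, and Protocol 10.1 plans visits about 28 and 56 days after the last dose. This stands as evidence that 56 days was intended. It does not remove the conflict, because 14.6 misreports the section it cites under a title that a site would consult for exactly this question.

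Four stronger readings are tempting, and the documents do not support them.

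- A reader might infer that expedited SAE notification also stops at EOT, because 14.7 begins "If an SAE occurs during the reporting period, the investigator must immediately". But 14.5.1 sets 56 days for SAEs and then sends the form for every SAE through the 14.7 time frame. SAEs are thus largely protected.
- A reader might use the half-life in Protocol 7.3 to argue that the omitted days are still exposed time. Those values come from healthy postmenopausal women after a first dose, at 0.0625 to 0.25 mg/kg, and do not give residual levels in this trial.
- A reader might conclude that the loss falls mainly on early stoppers, in whom late events matter most. With EOT at day 28 every patient loses the same 28 days and only the share differs. Nothing in the documents says that late events matter more in that group.
- A reader might want pre-dose SAEs added to 14.5.1. Section 14.5 already requires an SAE form for SAEs and refers to CRF completion guidelines that are not available here. Entering these events as AEs would also make them TEAEs under the present SAP wording.

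**Conclusion.** The inconsistency is real and is in current text. It concerns mainly non-serious AEs. A site that follows 14.6 and takes the EOT visit as the end of treatment leaves out 28 (21 to 35) of the 56 post-dose days. The upper bound of 56 days needs the treatment period to end at the last dose itself.

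The percentages assume no dose delays and count A536-06 time only. SAP 4.1 pools base-study data for patients who rolled over directly, so their share of the combined window is smaller. A patient who stops after a long dose hold may have EOT later than day 35 and lose less. The percentages are also not a loss of AEs: the documents give no AE rate, and SAP 5.8.1 counts each patient once per term, so the effect on crude incidence after long treatment is probably small. How many sites follow 14.6 is unknown. The point should be corrected because it affects capture for the primary endpoint, but it does not invalidate the trial.

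**What to change.** **Protocol.**

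- Reword 14.6 so that AEs and SAEs are recorded in the CRF through 56 days after the last dose of ACE-536.
- State that this is the reporting period meant in 14.7, and keep the 3-year rule for malignancy and premalignant lesions as a named exception.
- In 14.5 and 14.5.1, replace the EOS label on day 56, either with the day count alone or with a reference to PTFU.
- Reconcile the early-discontinuation EOS timing in 9.4 (and SAP 3.2) with 12.6 and SAP 5.1.

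**SAP 5.8.1.** Define TEAEs by onset from the first dose through last dose + 56 days, in place of all AEs collected. State which study's first dose applies to patients who rolled over directly. SAP 5.12.2 already imputes partial AE dates to decide whether an event is treatment emergent, which has a purpose only if there is a dated window. The definition also keeps later events, from sites that collect beyond day 56, out of the TEAE tables. It cannot restore events that were never recorded, so the protocol change is the essential part.

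**Cost.** A few wording changes in the protocol and a revised SAP definition. The 56-day window is already in 14.5 and the SAP, and PTFU is already scheduled, so no new visit is needed.

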14.7. Notification about Serious Adverse Events

If an SAE occurs during the reporting period, the investigator must immediately (i.e. within a maximum 24 hours after becoming aware of the event) inform the sponsor via the CRO by telephone, fax, or e-mail.

All written reports should be transmitted using the study specific SAE Report Form, which must be completed by the investigator following specific completion instructions. Names, addresses, telephone and fax numbers for SAE reporting are located on the SAE Report Form and in the completion instructions provided in the Study Manual. When an SAE (or follow up information) is reported by telephone, a written report must be sent immediately thereafter by fax or e-mail. Reporting procedures and timelines for follow up information are the same as for the initially reported SAE.

Relevant pages from the CRF may be provided in parallel (e.g., medical history, concomitant therapy). In all cases, the information provided in the SAE Report Form must be consistent with the data that are recorded in the corresponding sections of the CRF.

The investigator/reporter must respond to any request for follow up information or to any question the Sponsor or designee may have on the AE within the same timelines as described for initial reports. This is necessary to permit a prompt assessment of the event by the Sponsor and (as applicable) to allow the Sponsor to meet regulatory timelines associated with expedited reporting obligations.

Requests for follow up will usually be made by the responsible clinical research associate or Medical Monitor, or an Acceleron pharmacovigilance representative who may contact the investigator directly to obtain clarification on a particularly critical event.

14.7.1. Safety Reporting to Health Authorities, Independent Ethics Committees Institutional Review Boards and Investigators

The Sponsor will send appropriate safety notifications to Health Authorities in accordance with applicable laws and regulations.

The investigator must comply with any applicable site-specific requirements related to the reporting of SAEs involving his/her patients to the IEC that approved the study.

In accordance with ICH and GCP guidelines, the Sponsor will inform the investigator of “findings that could adversely affect the safety of patients, impact the conduct of the study, or alter the IEC’s approval/favorable opinion to continue the study.”

The Sponsor will inform the investigator of AEs that are both serious and unexpected and are considered to be related to ACE-536 (“suspected unexpected serious adverse reactions” or SUSARs). The investigator should place copies of these Safety Reports in the Investigator Site File. National regulations with regard to Safety Report notifications to investigators will be followed.

When specifically required by regulations and guidelines, the Sponsor will provide appropriate Safety Reports directly to the concerned lead IEC and will maintain records of these notifications. When direct reporting by the Sponsor is not clearly defined by national or site-specific regulations, the investigator will be responsible for promptly notifying the

concerned IEC of any Safety Reports and for filing copies of all related correspondence in the Investigator Site File.

For studies covered by the European Union Clinical Trials Directive 2001/20/EC, the Sponsor's responsibilities regarding the reporting of SAEs/SUSARs will be carried out in accordance with that Directive and with the related Detailed Guidances.

15. STATISTICS

15.1. Analysis Populations

Analysis Populations:

The modified Intent-to-Treat (mITT) Population: All patients enrolled in the study who received at least one dose of ACE-536.

Efficacy Evaluable (EE) Population: All patients administered at least one dose of ACE-536 and have 1) at least three hemoglobin assessments over an 8-week period, not influenced by transfusion, in NTD patients, OR, 2) at least 8 consecutive weeks of transfusion frequency data in TD patients.

Pharmacokinetics Population: All patients who received at least 1 dose of ACE-536 during Study A536-06 and have sufficient serum ACE-536 values for PK analysis.

15.2. Statistical Plan

Summary statistics will be presented for continuous/quantitative variables, by way of number of patients (n), mean, standard deviation (SD), median, minimum and maximum and by way of group frequencies and percentages for categories of qualitative variables. Percentages will be calculated using the total patients per treatment / subgroup. 95% confidence intervals (CIs) will be presented as applicable.

All patient data will be presented in separate data listings.

15.2.1. Patient Accountability and Demographics

Exposure to study drug and reasons for discontinuation of study will be tabulated, and demographics will be presented using descriptive statistics (i.e., mean, SD, median, and range).

15.2.2. Primary Endpoint Analysis

To assess clinical safety, all AEs, vital sign measurements and clinical laboratory information will be summarized. AEs will be coded using the Medical Dictionary for Regulatory Activities (MedDRA). Changes from baseline for clinical laboratory values and vital signs will be summarized over time. Descriptive statistics and shift tables will be generated as appropriate. Disposition rates will be summarized.

15.2.3. Secondary Analysis

All efficacy analyses will be performed for the EE and mITT populations.

Efficacy will be evaluated by determining the proportion of β -thalassemia patients who have an erythroid response, defined as 1) a mean hemoglobin increase ≥ 1.0 g/dL or ≥ 1.5 g/dL over an 8-week or 12-week period as compared to baseline, not influenced by RBC transfusion in NTD patients or 2) $\geq 20\%$ or $\geq 50\%$ reduction in RBC transfusion burden over an 8-week or 12-week period as compared to the 8-week or 12-week period pretreatment in TD patients.

Baseline hemoglobin for NTD patients will be the average of two or more measurements performed during the screening period for base study A536-04 (for patients without treatment

interruption) or study A536-06 (for patients with treatment interruption). Hemoglobin measurements within 2 weeks following RBC transfusion will be excluded.

Transfusion burden for TD patients will be defined as the ratio of RBC transfusion units (or mLs) transfused during an interval divided by the duration of that interval, where the interval may be during the pretreatment period or the treatment plus follow-up period. The interval during the pretreatment period will be defined as the 8 or 12 weeks prior to Cycle 1 Day 1 of base study A536-04 (will also be analyzed using pretreatment period of study A536-06 for patients with treatment interruption). An interval during the treatment plus follow-up period will be defined as an 8-week or 12-week interval after Cycle 1 Day 1 of study A536-06.

The erythroid response, as defined above, will also be evaluated using other pre-treatment and on-treatment intervals and other % reductions in RBC units transfused, including 100% (transfusion-free).

The erythroid response will be summarized using both a point estimate and its exact 95% CI based on binomial distribution.

No direct comparison testing with concurrent or historical controls will be performed.

Analysis of other secondary efficacy/PD endpoints will include:

- Time to erythroid response and duration of erythroid response
- Change/percent change from pretreatment in mean transfusion burden in TD patients
- Change in mean hemoglobin level in NTD patients
- Change in pre-transfusion hemoglobin levels in TD patients (including analysis of patient subset with < 20% change in transfusion burden)
- Change from baseline in erythropoiesis parameters, including EPO, reticulocytes, nucleated RBCs, and soluble transferrin receptor
- Change from baseline in hemolysis parameters, including total/indirect bilirubin, and LDH
- Change from baseline in iron overload and iron metabolism parameters, including serum iron, total iron binding capacity (TIBC), transferrin, calculated transferrin saturation, soluble transferrin receptor, ferritin, non-transferrin bound iron (NTBI), hepcidin, iron chelation therapy use and LIC by MRI

The exploratory endpoints will include evaluation of biomarkers related to the TGF- β superfamily, quality of life, change in EMH mass size, change in spleen size, change in BMD, change in leg ulcer size, and change in the 6MWT distance in NTD patients.

All binary endpoints will be summarized using both a point estimate and its exact confidence interval based on the binomial distribution. The time-to-event type secondary endpoints will be

analyzed using Kaplan-Meier method to estimate the survival curve and median time to event and 95% CI.

